13.1.1.6 Study Drug Action Taken

The investigator will classify the study drug action taken with regard to the AE. The action taken will be classified according to the categories shown in Table 13-3.

Table 13-3 Classifications for Study Drug Action Taken With Regard to an AE

Classification	Definition
Dose not changed	Study drug dose not changed in response to an AE.
Dose reduced	Not applicable for this study
Drug interrupted	Study drug administration interrupted in response to an AE.
Drug withdrawn	Study drug administration permanently discontinued in response to an AE.
Not applicable	Action taken regarding study drug administration does not apply. "Not applicable" will be used in circumstances such as when the investigational treatment had been completed before the AE began and no opportunity to decide whether to continue, interrupt, or withdraw treatment is possible.

AE: adverse event.

13.1.1.7 Adverse Event Outcome

An AE will be followed until the investigator has determined and provided the final outcome. The outcome will be classified according to the categories shown in Table 13-4.

Table 13-4 Classifications for Outcome of an AE

Classification	Definition
Recovered/Resolved	Resolution of an AE with no residual signs or symptoms
Recovered/ Resolved With Sequelae	Resolution of an AE with residual signs or symptoms
Not Recovered/Not Resolved (Continuing)	Either incomplete improvement or no improvement of an AE, such that it remains ongoing
Fatal	Outcome of an AE is death. "Fatal" will be used when death is at least possibly related to the AE.
Unknown	Outcome of an AE is not known (e.g., a subject lost to follow-up)

AE: adverse event.

13.1.1.8 Treatment Given

The investigator ensures adequate medical care is provided to subjects for any AEs, including clinically significant laboratory values related to study drug. In addition, the investigator will describe whether any treatment was given for the AE. "Yes" is used if any treatment was given in response to an AE and may include treatments such as other medications, hospitalization, surgery, or physical therapy. "No" indicates the absence of any kind of treatment for an AE.

13.1.2 Serious Adverse Events

13.1.2.1 Definition of a Serious Adverse Event

An SAE is any AE that meets any of the following outcomes:

- Fatal (death, regardless of cause, that occurs during participation in the study or occurs after participation in the study and is suspected of being a delayed toxicity due to administration of the study drug)
- Life-threatening, such that the subject was at immediate risk of death from the reaction as it occurred
- Inpatient hospitalization or prolongation of hospitalization
- Persistent or significant disability/incapacity (disability is defined as a substantial disruption of a person's ability to conduct normal life functions)
- Congenital anomaly or birth defect
- Important medical event that, based upon appropriate medical judgment, may jeopardize the subject or may require medical or surgical intervention to prevent 1 of the outcomes listed above (e.g., an allergic bronchospasm requiring intensive treatment in an emergency room or at home)

If a subject has a hospitalization or procedure (e.g. surgery) for an event or condition that occurred before the subject signed the ICF, and the hospitalization or procedure was planned before the subject signed the ICF, the hospitalization or procedure should not be considered to indicate an SAE, unless an AE caused the hospitalization or procedure to be rescheduled sooner or to be prolonged relative to what was planned. In addition, hospitalizations clearly not associated with an AE (e.g., social hospitalization for purposes of respite care) should not be considered to indicate an SAE.

Clarification will be made between the terms “serious” and “severe,” because they are not synonymous. The term “severe” is often used to describe the intensity (severity) of a specific event, as in mild, moderate, or severe myocardial infarction. The event itself, however, may be of relatively minor medical significance, such as a severe headache. This is not the same as “serious,” which is based on subject/event outcome or action described above, and is usually associated with events that pose a threat to a subject's life or functioning. Seriousness, not severity, serves as a guide for defining expedited regulatory reporting obligations.

13.1.2.2 Documentation of Serious Adverse Events

All SAEs that occur after obtaining informed consent and assent (where applicable) through the Follow-up Visit, regardless of causality, will be reported by the investigator to Vertex GPS. In addition, all SAEs that occur after the Safety Follow-Up Visit and are considered related to study drug(s) will be reported to Vertex GPS **within 24 hours**.

SAEs will be recorded on the Vertex Organized Safety Information Collection Form (hereafter referred to as the “SAE Form”) using a recognized medical term or diagnosis that accurately reflects the event. SAEs will be assessed by the investigator for relationship to the

investigational study drug(s) and possible etiologies. On the Clinical Trials SAE Form, relationship to study drug(s) will be assessed only as related (includes possibly related) or not related (includes unlikely related), and severity assessment will not be required. For the purposes of study analysis, if the event has not resolved at the end of the study reporting period, it will be documented as ongoing. For purposes of regulatory safety monitoring, the investigator is required to follow the event to resolution and report to Vertex the outcome of the event using the Vertex Clinical Trials SAE Form.

13.1.2.3 Reporting Serious Adverse Events

The investigator is responsible for notifying the sponsor within 24 hours of identifying an SAE, regardless of the presumed relationship to the investigational study drug. The Vertex Clinical Trial SAE Form will be completed for new/initial events as well as to report follow-up information on previously reported events. Investigators are asked to report follow-up information as soon as it becomes available to ensure timely reporting to health authorities.

Please send completed SAE Forms to Vertex Global Patient Safety via

Email: [REDACTED] (Preferred Choice)

Or via Fax: [REDACTED]

Contact Telephone: [REDACTED]

13.1.2.4 Expedited Reporting and Investigator Safety Letters

Vertex, as study sponsor, is responsible for reporting suspected, unexpected, serious adverse reactions (SUSARs) involving the study drug(s) to all regulatory authorities and participating investigators in accordance with ICH Guidelines and/or local regulatory requirements, as applicable. In addition, Vertex, or authorized designee, will be responsible for the submission of safety letters to central independent ethics committees (IECs).

It is the responsibility of the investigator or designee to promptly notify the local IRB/local IEC of all unexpected serious adverse drug reactions involving risk to human subjects.

13.2 Administrative Requirements

13.2.1 Ethical Considerations

The study will be conducted in accordance with the current ICH GCP Guidelines, which are consistent with the ethical principles founded in the Declaration of Helsinki, and in accordance with local applicable laws and regulations. The IRB/IEC will review all appropriate study documentation to safeguard the rights, safety, and well-being of the subjects. The study will only be conducted at sites where IRB/IEC approval has been obtained. The protocol, Investigator's Brochure, sample ICF, advertisements (if applicable), written information given to the subjects (including diary cards), safety updates, annual progress reports, and any revisions to these documents will be provided to the IRB/IEC by the investigator or Vertex, as allowable by local applicable laws and regulations.

13.2.2 Subject Information and Informed Consent and Assent

After the study has been fully explained, written informed consent will be obtained from the subject or legal representative or guardian (if applicable), and assent will be obtained from the subject (if applicable), before study participation. The method of obtaining and documenting the informed consent and assent (if applicable) and the contents of the consent will comply with ICH GCP and all applicable laws and regulations and will be subject to approval by Vertex or its designee.

13.2.3 Investigator Compliance

No modifications to the protocol will be made without the approval of both the investigator and Vertex. Changes that significantly affect the safety of the subjects, the scope of the investigation, or the scientific quality of the study (i.e., efficacy assessments) will require IRB/IEC notification before implementation, except where the modification is necessary to eliminate an apparent immediate hazard to human subjects. Vertex will submit all protocol modifications to the required regulatory authorities.

When circumstances require an immediate departure from procedures set forth in the protocol, the investigator will contact Vertex to discuss the planned course of action. If possible, contact will be made before the implementation of any changes. Any departures from protocol will be fully documented in the source documentation and in a protocol deviation log.

13.2.4 Access to Records

The investigator will make the office and/or hospital records of subjects enrolled in this study available for inspection by Vertex or its representative at the time of each monitoring visit and for audits. The records will also be available for direct inspection, verification, and copying, as required by applicable laws and regulations, by officials of the regulatory health authorities (FDA and others). The investigator will comply with applicable privacy and security laws for use and disclosure of information related to the research set forth in this protocol.

13.2.5 Subject Privacy

To maintain subject confidentiality, all electronic case report forms (eCRFs), study reports, and communications relating to the study will identify subjects by assigned subject numbers. As required by federal regulations, the investigator will allow Vertex and/or its representatives access to all pertinent medical records to allow for the verification of data gathered in the eCRFs/SAE Forms and the review of the data collection process. The FDA (or other regulatory authority) may also request access to all study records, including source documentation, for inspection.

As applicable, in accordance with the Health Insurance Portability and Accountability Act and associated privacy regulations, a subject authorization to use personally identifiable health information may be required from each subject before research activities begin. This authorization document will clearly specify which parties will have access to a subject's personal health information, for what purpose, and for how long.

13.2.6 Record Retention

The investigator will maintain all study records according to ICH GCP guidelines and/or applicable local regulatory requirement(s), whichever is longest, as described in the Clinical Trial Agreement. If the investigator withdraws from the responsibility of keeping the study records, custody will be transferred to a person willing to accept the responsibility and Vertex will be notified.

13.2.7 Study Termination

At any time, Vertex may terminate this study in its entirety or may terminate this study at any particular site. In addition, for reasonable cause, either the investigators or their IRBs/IECs may terminate the study at their center.

Conditions that may lead to reasonable cause and warrant termination include, but are not limited to:

- Subject or investigator noncompliance
- Unsatisfactory subject enrollment
- Lack of adherence to protocol procedures
- Lack of evaluable and/or complete data
- Potentially unacceptable risk to study subjects
- Decision to modify drug development plan
- Decision by the FDA or other regulatory authority

Written notification that includes the reason for the clinical study termination is required.

13.3 Data Quality Assurance

Vertex or its designated representative will conduct a study site visit to verify the qualifications of each investigator, inspect clinical study site facilities, and inform the investigator of responsibilities and procedures for ensuring adequate and correct study documentation.

The investigator is required to prepare and maintain adequate and accurate case histories designed to record all observations and other data pertinent to the study for each study participant. Study data for each enrolled subject will be entered into a CRF by study site personnel using a secure, validated web-based electronic data capture (EDC) application. Vertex will have read-only access to site-entered clinical data in the EDC application.

Instances of missing, discrepant, or uninterpretable data will be queried with the investigator for resolution. Any changes to study data will be made to the CRF and documented in an audit trail, which will be maintained within the clinical database.

13.4 Monitoring

Monitoring and auditing procedures developed or approved by Vertex will be followed to comply with GCP guidelines. On-site checking of the eCRFs/SAE Forms for completeness and clarity, cross-checking with source documents, and clarification of administrative matters will be performed.

The study will be monitored by Vertex or its designee. Monitoring will be done by personal visits from a representative of Vertex, or designee (study site monitor), who will review the eCRFs/SAE Forms and source documents. The study site monitor will ensure that the investigation is conducted according to the protocol design and regulatory requirements.

13.5 Electronic Data Capture

Vertex will provide the study sites with secure access to and training on the EDC application sufficient to permit study site personnel to enter or correct information in the eCRFs on the subjects for which they are responsible.

An eCRF will be completed for each enrolled study subject. It is the investigator's responsibility to ensure the accuracy, completeness, clarity, and timeliness of the data reported in the subject's eCRF. Source documentation supporting the eCRF data will indicate the subject's participation in the study and will document the dates and details of study procedures, AEs, other observations, and subject status.

The investigator, or designated representative, will complete the eCRF as soon as possible after information is collected.

The audit trail entry will show the user's identification information and the date and time of any correction. The investigator must provide formal approval of all the information in the eCRFs, including any changes made to the eCRFs, to endorse the final submitted data for the subjects for whom the investigator is responsible.

Vertex will retain the eCRF data and corresponding audit trails. A copy of the final archival eCRF in the form of a compact disc or other electronic media will be placed in the investigator's study file.

[REDACTED]

[REDACTED]

3 INTRODUCTION

This SAP, which describes the planned final analyses for Study VX14-661-106, is based on the following:

- the approved clinical study protocol (Version 4.0, dated 06 May 2016),
- the approved electronic case report forms (eCRF) (Version 3.0, dated 14 October, 2015).

Study VX14-661-106 is a Phase 3, randomized, double-blind, placebo-controlled, parallel-group study designed to evaluate the efficacy and safety of tezacaftor in combination with ivacaftor (TEZ/IVA) in subjects aged 12 years and older with cystic fibrosis (CF), homozygous for the *F508del* mutation on the *cystic fibrosis transmembrane conductance regulator* (*CFTR*) gene (*F508del-CFTR* mutation).

This SAP (Methods) documents the planned final statistical analyses of efficacy and safety endpoints defined in the VX14-661-106 study protocol. It also documents analyses for additional efficacy and safety variables not specified in the protocol, which will provide supportive information for the scientific understanding of the drug entity.

The pharmacokinetic (PK) and pharmacodynamic (PD) characteristics of TEZ/IVA in the *F508del* homozygous population also will be evaluated in the study. The relevant PK and PD analyses, however, will not be documented in this SAP. Rather, PK and PD analyses will be documented separately in the clinical pharmacology analysis plan (CPAP) for the study.

In addition, some exploratory endpoints were described in the study protocol. Analyses of exploratory endpoints are outside of the scope of this SAP and will be documented separately.

The Vertex Biometrics Department will perform the statistical analysis of the efficacy and safety data; SAS (Version 9.2, or higher) will be used to generate all statistical outputs (tables, figures, listings, and datasets). The SAP will be finalized and approved prior to the final clinical data lock and treatment unblinding for the study. If the methods in this SAP differ from the methods described in the protocol, the SAP will prevail.

4 STUDY OBJECTIVES

4.1 Primary Objective

The primary objective of the study is to evaluate the efficacy of TEZ/IVA through Week 24 in subjects with CF who are homozygous for the *F508del* mutation on the *CF transmembrane conductance regulator* (*CFTR*) gene.

4.2 Secondary Objectives

The secondary objectives of the study are as follows:

- To evaluate the safety of TEZ/IVA through Week 24

- To investigate the pharmacokinetics (PK) of tezacaftor and its metabolites, M1 and M2 (M1-661 and M2-661, respectively), and of ivacaftor and its metabolite, M1 (M1-ivacaftor).

5 STUDY ENDPOINTS

5.1 Efficacy Endpoints

5.1.1 Primary Efficacy Endpoint

The primary endpoint is absolute change from baseline in percent predicted forced expiratory volume in 1 second (FEV1) through Week 24.

5.1.2 Secondary Efficacy Endpoints

The key secondary efficacy endpoints are as follows:

- Relative change from baseline in percent predicted FEV1 through Week 24
- Number of pulmonary exacerbations through Week 24
- Absolute change in body mass index (BMI) from baseline at Week 24
- Absolute change in the Cystic Fibrosis Questionnaire-Revised (CFQ-R) respiratory domain score from baseline through Week 24

The following are other secondary efficacy endpoints:

- Time-to-first pulmonary exacerbation through Week 24
- Absolute change in sweat chloride from baseline through Week 24
- Absolute change in BMI z-score from baseline at Week 24 (in subjects <20 years of age at time of screening)
- Absolute change in body weight from baseline at Week 24

5.2 Safety Endpoints

Safety and tolerability are secondary endpoints which will be evaluated as follows:

- Adverse events (AEs)
- Clinical laboratory values (hematology, serum chemistry, coagulation studies, vitamin levels, lipid panel, and urinalysis)
- Standard 12-lead electrocardiograms (ECGs)
- Vital signs
- Pulse oximetry
- Spirometry

5.3 Pharmacokinetic Endpoints

PK parameters are secondary endpoints, which will be assessed based on the PK of tezacaftor, M1-661, M2-661, ivacaftor, and M1-ivacaftor.

[REDACTED]

6 STUDY DESIGN

6.1 Overview of Study Design

This is a Phase 3, randomized, double-blind, placebo-controlled, parallel-group, multicenter study in subjects with CF who are homozygous for the *F508del-CFTR* mutation. This study is designed to evaluate the efficacy and safety of TEZ/IVA. The active treatment regimen will be comprised of a morning dose of a fixed-dose combination tablet of 100 mg tezacaftor/150 mg ivacaftor once daily (qd) and an evening dose of ivacaftor 150 mg to be taken approximately 12 hours after the morning dose. The placebo regimen will be visually matched tablets to be taken with the same schedule as the active treatment.

[figure not shown]
This study consists of a Screening Period, a Treatment Period, and a Safety Follow-up Visit. Approximately 490 subjects will be stratified by age at the Screening Visit (<18 versus ≥18 years of age), sex (male versus female), and FEV₁ severity determined during the Screening Period (<70% versus ≥70% predicted) and then randomized (1:1) to either TEZ/IVA or placebo as shown in [Figure 6-1](#).

Subjects who complete the Week 24 Visit will be offered the opportunity to enroll into the extension phase of Study 106, if they meet the relevant eligibility requirements.

All subjects will be required to complete study assessments for all scheduled visits, regardless of whether they have prematurely discontinued study drug treatment prior to Week 24 (see Protocol Section 8.1.4).

A schematic of the study design is shown in Figure 6-1.

Figure 6-1 Schematic of the Study Design

IVA: ivacaftor; q12h: every 12 hours; qd: once daily.

^a The Safety Follow-up Visit is scheduled to occur 28 (±7) days after the Week 24 Visit. The Safety Follow-up Visit is not required for subjects who complete the Week 24 Visit in this study, and are eligible and enroll in an extension study of TEZACAFTOR in combination with ivacaftor.

^b Approximately 490 subjects will be stratified by age at the Screening Visit (<18 versus ≥18 years of age), sex (male versus female), and FEV₁ severity determined during the Screening Period (<70% versus ≥70% predicted) and randomized (1:1) before the first dose of study drug on Day 1.

6.2 Sample Size and Power

The study is powered for both the primary endpoint (change from baseline in ppFEV₁) and a secondary endpoint of clinical interest (relative risk of pulmonary exacerbations).

The primary efficacy endpoint is the absolute change from baseline in percent predicted FEV₁ through Week 24.

The null hypothesis to be tested is that the mean absolute change from baseline in percent predicted FEV₁ through Week 24 is the same for TEZ/IVA and placebo. Assuming a common standard deviation (SD) of 8% in each arm, a sample size of 220 subjects in each treatment group will have at least 90% power to detect a treatment difference of 2.5% in percent predicted FEV₁ between treatment groups, using a 2-sided significance level of 0.05. If the above null hypothesis is rejected, the efficacy of TEZ/IVA will be considered established.

Power for pulmonary exacerbation:

Assuming the pulmonary exacerbation rate for placebo is 0.5 events in 24 weeks, with 220 subjects in each treatment group, the power to detect a 40% reduction in the pulmonary exacerbation rate in the active arm versus the placebo arm is about 92%. The power to detect a 33% reduction in the pulmonary exacerbation rate is about 78%.

This power calculation is based on an R simulation with 10,000 replications. To adjust for a 10% dropout, a total sample size of 490 subjects is needed.

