12.1 Sample Size and Power

The primary efficacy endpoint is the absolute change in percent predicted FEV₁ from baseline through Week 24.

The null hypothesis to be tested is that the mean change from baseline in percent predicted FEV₁ through Week 24 is the same for the 2 treatment arms. Assuming a common standard deviation (SD) of 8% and a 10% dropout rate, a sample size of 245 subjects in each treatment group will have at least 90% power to detect a treatment difference of 2.5% in percent predicted FEV₁ between treatment groups, using a 2-sided significance level of 0.05. If the above null hypothesis is rejected, the efficacy of VX-661/ivacaftor is considered established.

Power for pulmonary exacerbation:

Assuming the pulmonary exacerbation rate for placebo is 0.5 in 24 weeks, with 220 subjects in each treatment group, the power to detect a 40% reduction in the pulmonary exacerbation rate in the active arm versus the placebo arm is about 92%. The power to detect a 33% reduction in the pulmonary exacerbation rate is about 78%.

This power calculation is based on an R simulation with 10,000 replications.

To adjust for a 10% dropout, a total sample size of 490 subjects is needed.

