12.3.3.2 Analysis of Secondary Efficacy Variables

- **Relative change in percent predicted FEV₁ from baseline through Week 24:** Analysis of this variable will be similar to the primary analysis.
- **Number of pulmonary exacerbations through Week 24:** For number of pulmonary exacerbations, the treatment comparison will be carried out using a regression analysis for negative binomial distribution with treatment, sex, age group at baseline, and percent predicted FEV₁ severity determined at Screening as covariates. The log of the time spent in the study will be treated as the offset in the model. A stratified Wilcoxon rank-sum test, adjusted for sex, age group at baseline, and percent predicted FEV₁ severity determined at Screening will be performed as a sensitivity analysis.
- **Absolute change in BMI from baseline at Week 24:** Analysis for this variable will be similar to the primary analysis, with the addition of baseline BMI as a covariate.
- **Absolute change in the CFQ-R respiratory domain score from baseline through Week 24:** Analysis of this domain will be similar to the primary analysis, with the addition of the CFQ-R respiratory symptoms domain score at baseline as a covariate.
- **Time-to-first pulmonary exacerbation through Week 24:** Time-to-first pulmonary exacerbation will be analyzed using the Cox regression model. The model will include the main effect of treatment as well as covariates for sex, age group at baseline, and percent predicted FEV₁ severity determined at Screening. A subject without exacerbation before withdrawal or completion of the study will be considered censored at the time of withdrawal or completion of the study. If the proportional hazards assumption is violated, a stratified analysis will be conducted using stratified Cox regression. Additionally, Kaplan-Meier methods will be used to produce graphical presentations of the survival distributions (exacerbation-free survival) for each treatment arm and to estimate cumulative survival rates by treatment. Note: If the number of events is <5 in either treatment group, Cox regression will not be performed and analysis of time-to-first event will be restricted to Kaplan-Meier methods.
- **Absolute change in sweat chloride from baseline through Week 24:** Analysis of this variable will be performed using the same model as described for the absolute change in percent predicted FEV₁ from baseline, with the addition of baseline sweat chloride value as covariate.

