8.3.2.2 Analysis of Secondary Efficacy Endpoints

8.3.2.2.1 Analysis of Key Secondary Efficacy Endpoints

Relative change from baseline in ppFEV₁ through Week 24

Analysis for the relative change from baseline in ppFEV₁ through Week 24 will be similar to that for the primary analysis. The LS Mean (SE) of the overall treatment difference between TEZ/IVA and placebo in the relative change from baseline in percent predicted FEV₁ from Day 15 through Week 24 will be presented along with the 95% confidence interval and a 2-sided *P* value.

The LS Mean (SE) of within-treatment group relative change from baseline at each post-baseline visit along with the corresponding 95% CI and p-value will be estimated from the same MMRM model. The LS Mean (SE) of the treatment difference between TEZ/IVA and placebo at each post-baseline visit will be provided along with the corresponding 95% CI and p-value. The LS means (with 95% CI) at each post-baseline visit will also be plotted by treatment group. Summary statistics of raw values and absolute change from baseline in ppFEV₁ at each visit will be presented. The cumulative distribution of the average relative change from study baseline in ppFEV₁ through week 24 will be plotted by treatment group.

Number of pulmonary exacerbations through Week 24

A negative binomial generalized linear model will be used to compare the rates of pulmonary exacerbations over the 24-week treatment period for the two treatment groups. The estimated rate ratio and the associated 95% CI and p-value will be provided. In this model, the dependent variable will be the number of pulmonary exacerbations through Week 24, (including both on treatment events and events after treatment discontinuation). Treatment, sex, age group at screening (<18 vs. ≥ 18 years old), and baseline percent predicted FEV₁ will be included as covariates. The log of time spent in the study will be treated as the offset in this model. A log link function will be used in this model. If the model does not converge, the negative binomial regression model will be replaced with a Poisson regression model with the same covariates, offset variable, and link function.

Absolute change in BMI from baseline at Week 24

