8.3.2.2.2 Multiplicity adjustment

A hierarchical testing procedure will be used to control the overall Type I error for the multiple endpoints tested at $\alpha = 0.05$. For a test at any step to be considered statistically significant within the testing hierarchy, the test must be statistically significant at the 0.05 level, and all previous tests (if any) within the hierarchy must also be statistically significant. The testing hierarchy is as follows:

1. Absolute change from baseline in ppFEV₁ through Week 24
2. Relative change from baseline in ppFEV₁ through Week 24
3. Number of pulmonary exacerbations through Week 24
4. Absolute change in BMI from baseline at Week 24
5. Absolute change in CFQ-R respiratory domain score from baseline through Week 24

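### Does the exacerbation power of about 92% and 78% need restating because the simulated count distribution and dispersion are not given?

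*SAP*

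**What the plan says.** SAP 6.2 opens with the claim that "The study is powered for both the primary endpoint" and for pulmonary exacerbations. For exacerbations it assumes 0.5 events per subject in 24 weeks on placebo and 220 subjects per arm, and states that "the power to detect a 40% reduction in the pulmonary exacerbation rate in the active arm versus the placebo arm is about 92" per cent. Protocol 12.1 has the same inputs and adds, as the SAP also does, that "The power to detect a 33% reduction in the pulmonary exacerbation rate is about 78" per cent. The only method given is "This power calculation is based on an R simulation with 10,000 replications". Both sections then allow for 10% dropout, giving 490 subjects in total.

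The analysis is specified separately. In Protocol 12.3.3.2, "the treatment comparison will be carried out using a regression analysis for negative binomial distribution". In SAP 8.3.2.2.1, "A negative binomial generalized linear model will be used to compare the rates of pulmonary exacerbations over the 24-week treatment period"; if that model does not converge, "the negative binomial regression model will be replaced with a Poisson regression model". Exacerbations are third in the testing order of SAP 8.3.2.2.2, where for any step to count, "all previous tests (if any) within the hierarchy must also be statistically significant".

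**The concern.** A count endpoint's power depends on how much rates vary between subjects. Poisson counts assume no such variation; a negative binomial model is chosen because some is expected. Planning on Poisson counts and then analysing with a negative binomial model would make the quoted power a best case for the given number of subjects. The text does not say which distribution was simulated, and 2-sided 0.05 is written only in the FEV1 paragraph. The stated figures lie close to what Poisson counts give, which raises the suspicion.

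The stake would be the claim that the trial is powered for exacerbations. A non-significant result at that step also ends formal testing of BMI and the CFQ-R respiratory score.

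**Working it through.** **Inputs.** From SAP 6.2: placebo mean m0 = 0.5, n = 220 per arm, reductions of 40% (rate ratio RR = 0.60) and 33% (RR = 0.67, or 2/3 if read as one third). From SAP 6.3: 245 randomised per arm. Assumed: 2-sided 0.05, and dispersion k with variance m + k·m². The documents give no k, so a range is shown.

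**Reproducing the plan's figures.** With Poisson counts the arm totals have means 220 × 0.5 = 110 on placebo and 66 (RR 0.60), 73.7 (RR 0.67) or 73.3 (RR 2/3) on active. Exact enumeration of the totals gives:

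| RR | Wald | Score | Likelihood ratio | Stated |
|---|---|---|---|---|
| 0.60 | 91.5% | 91.6% | 91.7% | about 92% |
| 0.67 | 76.5% | 76.6% | 76.8% | about 78% |
| 2/3 | 77.4% | 77.6% | 77.7% | about 78% |

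The 40% figure reproduces. The 33% figure is close, and closest if 33% means one third.

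**Effect of overdispersion.** Var(log RR) = (1/m0 + 1/m1 + 2k)/n, and power = Φ(|log RR|/√Var − 1.96). For RR 0.60 and k = 0 at n = 220: Var = (2 + 3.333)/220 = 0.02424, √Var = 0.1557, and 0.5108/0.1557 − 1.96 = 1.321, which gives 90.7%. This is about one point below the exact Poisson result, so the formula reads slightly low from the start. With k = 0.5, Var = (5.333 + 1)/220 = 0.02879, and power is 85.3%.

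| k (assumed) | n = 220: 40% / 33% to one third | n = 245, full follow-up: 40% / 33% to one third |
|---|---|---|
| 0 | 90.7% / 75.8-76.7% | 93.3% / 80.2-81.0% |
| 0.15 | 89.1% / 73.4-74.3% | 92.1% / 77.8-78.7% |
| 0.25 | 88.0% / 71.8-72.7% | 91.2% / 76.3-77.2% |
| 0.5 | 85.3% / 68.0-69.0% | 88.8% / 72.7-73.6% |
| 1.0 | 79.9% / 61.3-62.3% | 84.0% / 66.0-67.0% |

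Simulating the negative binomial test without covariates at n = 220 (20,000 replicates per cell) gives 91.2%, 89.4%, 86.2% and 81.4% for RR 0.60 at k = 0, 0.25, 0.5 and 1.0, a little above the formula. At k = 0 the test itself costs almost nothing; any loss comes from the variation in rates.

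**Which n applies.** Using 220 treats the 10% dropouts as contributing nothing. Protocol 8.1.2 and 8.1.4 keep subjects who stop treatment in follow-up through Week 24. SAP 8.3.2.2.1 counts their later events and enters partial follow-up through the log-time offset. The two columns therefore bracket the information the trial would have.

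**Other readings of the stated pair.** A negative binomial simulation with 245 per arm and k about 0.15 fits (table above). So, roughly, does 220 per arm at 1-sided 0.05 with k of 0.4 to 0.5: 91.4-92.1% and 78.3-80.3%. The figures do not show that Poisson counts were simulated.

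**Primary endpoint.** With SD 8, difference 2.5 and 220 per arm: 2.5/(8 × √(2/220)) − 1.96 = 1.317, or 90.6%, in line with the stated 90%. Dropout: 220/0.9 = 244.4, so 245 per arm and 490 in total.

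**The case for a change.** The best case for a change is that the exacerbation calculation lacks the one input that decides what its result means. The FEV1 calculation states its SD; this one states no variance assumption, although the planned model exists to handle extra variation. If k were 1.0, the chance of missing a true 40% reduction would be about 20% at 220 per arm, or 16% at 245, against the stated 8%. The remedy would be a few lines and one rerun.

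The omission stands: neither document gives the simulated distribution or dispersion. The sensitivity to k is also real. What does not stand is the step from there to an error. A k of 1.0 has no anchor in the documents, and a moderate k is roughly absorbed by the subjects randomised above 220. Of the other missing items, the choice of test hardly matters. A 1-sided test would be a strained reading, since 2-sided 0.05 is used in the same section and SAP 8.3.2.2.1 reports the rate ratio with a 95% confidence interval.

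**Conclusion.** This is missing detail in a planning statement, not a fault in the plan. The stated power is close to what Poisson counts give at 220 per arm and 2-sided 0.05, and is also compatible with mild overdispersion at 245 per arm. A material shortfall needs a k of about 0.5 or more: at k = 0.5 the 40% case has 85.3% to 88.8% power and the 33% case 68.0% to 73.6%, depending on how much follow-up is kept. Those values rest on an assumed k, a 2-sided 0.05 test, no covariate adjustment and equal follow-up within each column.

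Filling the gap would leave everything that matters as it is. The negative binomial model estimates dispersion from the trial's own counts, so the validity of the test does not depend on what was simulated at planning. The sample size rests independently on FEV1. The testing order controls Type I error whatever the power at step 3. A sponsor revising these sections anyway could usefully name the distribution and dispersion, but no analysis, sample size or conclusion would move.
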